10.2 Appendix B Censor rule for TTR

No.	Situation	Events or Censor	Analysis date*
1	CR, PR before PD, Death, alternative anti-cancer therapy or missed two consecutive assessment.	Events	First CR, PR date
2	No CR/PR/ alternative anti-cancer therapy/ missed two consecutive assessment/PD/Death	Censor	Last assessment date
3	No CR/PR, have PD or Death	Censor	First date of PD or Death
4	No CR/PR before alternative anti-cancer therapy	Censor	Last assessment date before initiating alternative anti-cancer therapy
5	No CR/PR before missed two consecutive assessment	Censor	Last assessment date before the missed two consecutive assessment

* If there are multiple assessment date on one tumor assessment, choose the earliest assessment date when overall response is PD, and choose the latest assessment date when overall response is CR/PR/SD.

10.3 Appendix C Censor rule for TTP

No.	Situation	Events or Censor	Analysis date*
1	No baseline assessment	Censor	First dose date
2	No post-baseline assessment, no Death	Censor	First dose date
3	PD during the study (except #5, #7)	Events (PD)	PD date
4	Any kind of Death (except #5, #7)	Censor	Death date
5	PD or Death after missed two consecutive assessment	Censor	Last assessment date before the missed two consecutive assessment
6	Have at least one post-baseline assessment, no PD, no Death	Censor	Last assessment date
7	Initiating alternative anti-cancer therapy	Censor	Last assessment date before initiating alternative anti-cancer therapy

* If there are multiple assessment date on one tumor assessment, choose the earliest assessment date when overall response is PD, and choose the latest assessment date when overall response is CR/PR/SD.

10.4 Appendix D. Laboratory Grading and Notable Vital Sign Values

Laboratory Values

Safety laboratory values below a distinct limit (eg. detection limit, documented as "< [limit]") will be substituted by half of the limit and values above a distinct limit (documented as "> [limit]") will be substituted by the limit itself for all analyses.

A Grade (based on CTC AE version 5.0 [v5.00: November 27, 2017]) will be assigned to each laboratory result as detailed in Table 2. Depending on the toxicity definition, the same result may be assigned to two grading for deviations towards higher or lower values. In case no lower limit of normal is provided for the absolute lymphocyte, neutrophils or leukocyte counts it will not be differentiated between grade 1 and grade 0 results for these parameters. Values not meeting any of the criteria will be assigned a grade 0.

Table 1. Grading of Select Laboratory Parameters

Laboratory Parameter [Unit]	Grade 1	Grade 2	Grade 3	Grade 4
Lymphocytes [G/L]	0.8 - < LLN	0.5 - < 0.8	0.2 - < 0.5	< 0.2
Neutrophils [G/L]	1.5 - < LLN	1.0 - < 1.5	0.5 - < 1.0	< 0.5
Leukocytes [G/L]	3.0 - < LLN	2.0 - < 3.0	1.0 - < 2.0	< 1.0
Platelets [G/L]	75 - < LLN	50 - < 75	25 - < 50	< 25
Hemoglobin [g/L]*	100 - < LLN	80 - < 100	< 80	not defined
Albumin [g/L]	30 - < LLN	20 - < 30	< 20	not defined
AST*	> ULN - 3*ULN	> 3*ULN - 5*ULN	> 5*ULN - 20*ULN	> 20*ULN
ALT *	> ULN - 3*ULN	> 3*ULN - 5*ULN	> 5*ULN - 20*ULN	> 20*ULN
GGT	> ULN - 2.5*ULN	> 2.5*ULN - 5*ULN	> 5*ULN - 20*ULN	> 20*ULN
Bilirubin	> ULN - 1.5*ULN	> 1.5*ULN - 3*ULN	> 3*ULN - 10*ULN	> 10*ULN
Fibrinogen^	%change of BL <25% decrease or 0.75*LLN - < LLN	25%- <50% decrease of BL or < 75*LLN - 0.5*LLN	50% - <75% decrease of BL or < 0.5* LLN - 0.25*LLN	>= 75% decrease of BL or < 50mg/dL or < 0.25*LLN
Calcium [mmol/L]*	2.0 - < LLN	1.75 - < 2.0	1.5 - < 1.75	< 1.5
Potassium [mmol/L]*	not defined	3.0 - < LLN	2.5 - < 3.0	< 2.5
Lipase	> ULN - 1.5*ULN	> 1.5*ULN - 2.0*ULN	> 2.0*ULN - 5.0*ULN	> 5.0*ULN
Amylase	> ULN - 1.5*ULN	> 1.5*ULN - 2.0*ULN	> 2.0*ULN - 5.0*ULN	> 5.0*ULN

BL: baseline value, LLN: Lower limit of normal, ULN: Upper limit of normal

*: Clinical criteria from CTC AE 5.0 grading were not considered in order to assign grades

^: In case of conflicting criteria the higher grade will be assigned, % change only used when baseline is <LLN

Vital Signs

Notable values for vital signs are defined according to the following table:

Table 2. Notable Abnormalities of Vital Signs

Vital Sign	Notable Abnormalities
Pulse rate/Heart rate (bpm)	>100 <60
Respiratory Rate (bpm)	>24

Vital Sign	Notable Abnormalities	
	<12	
Blood pressure (mmHg)	Systolic	160
		90
	Diastolic	105
		50
Weight (kg)	change from baseline >10% (in both directions)	
Body temperature (°C)	> 39	

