Grade 1 (>ULN - 1.5 x ULN if baseline was normal; > 1.0 - 1.5 x baseline if baseline was abnormal)	Maintain dose level

Recommended dose modifications for HH2710	
Worst toxicity CTCAE Grade^a (value)	Recommended dose modifications any time during a cycle of therapy, including intended day of dosing^b
Grade 2 (>1.5 - 3.0 x ULN if baseline was normal; >1.5 - 3.0 x baseline if baseline was abnormal)	Discontinue dose until resolved to \leq Grade 1, then: 
 - If resolved in \leq 7 days, then maintain dose level - If resolved in > 7 days, then \downarrow 1 dose level
Grade 3 (>3.0 - 10.0 x ULN if baseline was normal; >3.0 - 10.0 x baseline if baseline was abnormal)	Discontinue dose until resolved to \leq Grade 1, then: 
 - If resolved in \leq 7 days, then \downarrow 1 dose level - If resolved in > 7 days, then discontinue patient from study drug treatment
Grade 4 (>10.0 x ULN if baseline was normal; >10.0 x baseline if baseline was abnormal)	Permanently discontinue HH2710
AST or ALT	
Grade 1 (>ULN - 3.0 x ULN if baseline was normal; 1.5 - 3.0 x baseline if baseline was abnormal)	Maintain dose level
Grade 2 (>3.0 - 5.0 x ULN if baseline was normal; >3.0 - 5.0 x baseline if baseline was abnormal)	Maintain dose level
Grade 3 (>5.0 - 20.0 x ULN if baseline was normal; >5.0 - 20.0 x baseline if baseline was abnormal)	Discontinue dose until resolved to \leq Grade 1 (or \leq Grade 2 if liver metastases present), then: 
 - If resolved in \leq 7 days, then maintain dose level - If resolved in > 7 days, then \downarrow 1 dose level
Grade 4 (>20.0 x ULN if baseline was normal; >20.0 x baseline if baseline was abnormal)	Permanently discontinue HH2710

Recommended dose modifications for HH2710	
Worst toxicity CTCAE Grade^a (value)	Recommended dose modifications any time during a cycle of therapy, including intended day of dosing^b
ALT/AST > 3 ULN and concomitant TBL > 2 ULN in the absence of evidence of biliary obstruction (i.e., significant elevation of ALP) or some other explanation of the injury (e.g., viral hepatitis, alcohol hepatitis) of any duration (i.e. Hy's law)	Permanently discontinue HH2710
Investigation (metabolic)**	
amylase and/or lipase elevation	
Grade 1 (> ULN - 1.5 x ULN)	Maintain dose level
Grade 2 (>1.5-2.0xULN; >2.0-5.0xULN and asymptomatic)	Maintain dose level

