Grade 3 (>2.0 - 5.0 x ULN with signs or symptoms; >5.0 x ULN and asymptomatic)	Discontinue dose of until resolved to Grade \leq 2, then: 
 - If resolved in \leq 7 days, then maintain dose level - If resolved in > 7 days, then \downarrow 1 dose level
Grade 4 (>5.0 x ULN and with signs or symptoms)	Permanently discontinue HH2710.
Cardiac general	
Grade 1 or 2	Maintain dose level
Grade 3	Discontinue dose until resolved to \leq Grade 1, then \downarrow 1 dose level
Grade 4	Discontinue dose and discontinue patient from study drug treatment

Recommended dose modifications for HH2710	
Worst toxicity CTCAE Grade^a (value)	Recommended dose modifications any time during a cycle of therapy, including intended day of dosing^b
Electrocardiogram QT corrected (QTc) interval prolonged	
Grade 1 or 2 Heart Failure	Maintain dose level
Grade 3 Heart Failure	Permanently discontinue HH2710 and discontinue patient from study drug treatment
Grade 4 Heart Failure	Permanently discontinue HH2710 and discontinue patient from study drug treatment
Grade 2 Ejection Fraction (EF) Decreased (resting EF: 50-40%; or 10-19% drop from baseline)	Discontinue HH2710 until ejection fraction returns to a value greater than the institutional lower limit of normal and the absolute decrease from baseline is $\leq 15\%$, then maintain dose level.
Grade 3-4 EF Decreased (resting EF 39-20%; or $\geq 20\%$ drop from baseline)	Permanently discontinue HH2710
Grade 1 and 2 (QTcF 450-500ms)	Maintain dose level
Grade 3 (QTcF ≥ 501 ms on at least two separate ECGs)	Discontinue dose until resolved to Grade ≤ 2 , then: 
 - If resolved in ≤ 7 days, then maintain dose level - If resolved in > 7 days, then $\downarrow 1$ dose level
Grade 4 (QTcF ≥ 501 ms or > 60 ms change from baseline and Torsades de pointes or polymorphic ventricular tachycardia or signs/symptoms of serious)	Permanently discontinue HH2710
Eye disorders	
Retinal vein occlusion (RVO)	Permanently discontinue HH2710.

Recommended dose modifications for HH2710	
Worst toxicity CTCAE Grade^a (value)	Recommended dose modifications any time during a cycle of therapy, including intended day of dosing^b
Other Grade 1 or 2 eye AEs	Discontinue dose until resolved to baseline, HH2710 could be restarted after assessed by ophthalmologist and investigator, maintain dose level or one dose level reduced as clinically indicated.

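### The laboratory grading grid in SAP Appendix D gives higher grades than protocol Table 6-8 for asymptomatic lipase/amylase above 2 x ULN, and can do so for AST, ALT and bilirubin when baseline is abnormal

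*SAP*

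**What the plan says.** SAP Appendix D states that a CTCAE v5.0 grade "will be assigned to each laboratory result as detailed in Table 2". The SAP's list of tables calls the laboratory grid Table 2, although the heading printed over it reads Table 1.

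In that grid the Grade 3 band for both lipase and amylase is "> 2.0*ULN - 5.0*ULN", and anything above 5 x ULN is Grade 4. Symptoms play no part. AST, ALT and bilirubin are graded on multiples of ULN, with no rule for an abnormal baseline. A footnote reads "Clinical criteria from CTC AE 5.0 grading were not considered in order to assign grades". Its asterisk is attached to hemoglobin, AST, ALT, calcium and potassium, but not to lipase, amylase or bilirubin.

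Protocol Section 6.3.1, Table 6-8, is also tied to CTCAE v5.0. For amylase and lipase it has "Grade 2 (>1.5-2.0xULN; >2.0-5.0xULN and asymptomatic", then "Grade 3 (>2.0 - 5.0 x ULN with signs or symptoms; >5.0 x ULN and asymptomatic", then "Grade 4 (>5.0 x ULN and with signs or symptoms". For AST or ALT the Grade 3 row is "Grade 3 (>5.0 - 20.0 x ULN if baseline was normal; >5.0 - 20.0 x baseline if baseline was abnormal", and for bilirubin the Grade 2 row is "Grade 2 (>1.5 - 3.0 x ULN if baseline was normal; >1.5 - 3.0 x baseline if baseline was abnormal". The other AST/ALT and bilirubin grades follow the same two-part pattern.

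Inclusion criterion 9 (protocol Section 5.2) admits abnormal baselines: AST/ALT up to 3 x ULN, or 5 x ULN with liver involvement by tumor, and bilirubin up to 1.5 x ULN.

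**The concern.** Both documents claim the same CTCAE version, yet one laboratory result can carry two different grades. The SAP does not signal this where it matters. Symptoms decide the grade for lipase and amylase above 2 x ULN, but those rows lack the asterisk, so they read as full CTCAE grades. AST and ALT do carry it, but a multiple of baseline is not a clinical criterion, so the footnote does not cover that omission. Baseline logic was not ruled out in principle: the fibrinogen row of the same grid uses it. SAP Section 8.12, which records changes as small as decimal places, does not mention the difference.

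Clinical laboratory values are part of the Phase I primary safety endpoint, and protocol Section 1.2.2 names liver and pancreatic toxicity as important potential risks. Dose levels are small. The escalation levels held 3 or 4 patients at the January 2022 cutoff, so if the derived grades were tabulated by dose level, one re-graded patient would be 1/4 = 25% to 1/3 = 33% of such a level.

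**Working it through.** The plan gives no figure to reproduce here. The check applies both grading rules to the same values. Inputs are the Appendix D grid, Table 6-8 and inclusion criterion 9. An abnormal baseline is read as one above ULN.

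**1. Lipase and amylase**

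| Value (x ULN) | SAP | Table 6-8, asymptomatic | Table 6-8, symptomatic |
|---|---|---|---|
| 1.8 | 2 | 2 | 2 |
| 3 | 3 | 2 | 3 |
| 5 | 3 | 2 | 3 |
| 5.5 | 4 | 3 | 4 |
| 8 | 4 | 3 | 4 |

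The grids agree up to 2 x ULN and for all symptomatic values. Above 2 x ULN without symptoms the SAP is always exactly one grade higher.

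**2. AST and ALT, baseline above ULN**

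The SAP grades the result v (in x ULN) against cutpoints 1, 3, 5 and 20. Table 6-8 grades the ratio v/b, where b is the baseline in x ULN; Grade 1 starts at 1.5 and the higher cutpoints are 3, 5 and 20.

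| Baseline b | Result v | v/b | SAP | Table 6-8 |
|---|---|---|---|---|
| 2 | 6 | 3.0 | 3 | 1 |
| 3 | 4 | 1.33 | 2 | below 1 |
| 4 | 4 | 1.0 | 2 | below 1 |
| 4 | 5.5 | 1.375 | 3 | below 1 |
| 5 | 6 | 1.2 | 3 | below 1 |
| 2 | 12 | 6.0 | 3 | 3 |

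A three-grade gap needs v > 5 together with v/b < 1.5, so b > 5/1.5 = 3.33 x ULN. (SAP Grade 4 against Table 6-8 Grade 1 would need v > 20 with v/b at most 3, so b > 20/3 = 6.67, which is not eligible.) Since 3.33 exceeds 3, eligibility allows the three-grade gap only in patients with liver involvement. At baselines up to 3 x ULN the gap is at most two grades.

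**3. Bilirubin, baseline above ULN**

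Both rules use cutpoints 1, 1.5, 3 and 10, the SAP on v and Table 6-8 on v/b.

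| Baseline b | Result v | v/b | SAP | Table 6-8 |
|---|---|---|---|---|
| 1.5 | 1.5 | 1.0 | 1 | below 1 |
| 1.5 | 4 | 2.67 | 3 | 2 |
| 1.2 | 4 | 3.33 | 3 | 3 |

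**4. Direction over the eligible range**

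When b > 1, v/b is smaller than v and no Table 6-8 cutpoint is lower than the SAP's, so the SAP grade cannot be the lower one. A scan of results from 0.10 to 30 x ULN confirmed this. For AST/ALT baselines of 1.01 to 5 x ULN the SAP was never lower and at most three grades higher. For bilirubin baselines of 1.01 to 1.5 x ULN it was never lower and at most one higher. With a normal baseline the two rules are identical for AST, ALT and bilirubin.

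**5. Where the grades go**

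SAP Section 8.8.1.3 plans observed values and changes by visit, shifts in clinical significance, liver elevations in x ULN categories and a listing of abnormal findings. None is by laboratory grade, and the section does not cite Appendix D. The vital-signs section, 8.8.1.4, does cite it.

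**The case against.** The strongest objection is that nothing depends on the grid. The SAP lists its laboratory outputs and none uses these grades. AE severity is judged event by event under CTCAE v5.0 (protocol Section 8.1.3, SAP Section 8.8.1.1). DLTs have their own criteria in protocol Table 6-6, which deal separately with asymptomatic lipase and amylase, and SAP Section 8.8.1.2 only lists them. Table 6-8 is a treatment-modification table, not an analysis specification, so silence in SAP Section 8.12 need not be a concealed change of analysis. Laboratory and AE grades would not match one to one anyway, because under protocol Section 8.1 an abnormal result becomes an AE only under certain conditions and may be absorbed into a diagnosis. The SAP adds that the study stopped early and that many analyses may not be run.

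Most of this stands and it limits the point. A reader might infer that the planned safety tables will contradict each other, or that DLT counts, the MTD or the RP2D are affected. The documents support neither: no planned table shows the grades, and nothing links Appendix D to AE severity or dose decisions. A reader might also extend the baseline rule to GGT, but Table 6-8 has no GGT row.

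What the objection does not remove is the conflict itself. Appendix D sets a grade for every result and attributes it to CTCAE v5.0, while the protocol's table under the same version gives a different grade.

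**Conclusion.** The conflict is real but minor. For asymptomatic lipase or amylase above 2 x ULN the SAP grade is one too high relative to Table 6-8. For patients with a baseline above ULN it can be up to three grades higher for AST/ALT and up to one for bilirubin. All other comparisons made here agree. The error is confined to the SAP-derived laboratory grades and to any display of them.

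This rests on reading an abnormal baseline as above ULN, on baselines staying within the eligibility limits, and on comparing the two documents only; the CTCAE text was not consulted. The documents do not say how many patients would be re-graded.

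**What to change.** In SAP Appendix D:

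- Grade lipase and amylase on the numeric value using the asymptomatic bands of Table 6-8: above 2 and up to 5 x ULN is Grade 2, above 5 x ULN is Grade 3. Add a footnote that symptoms are not considered and that symptomatic cases are graded in the AE data.
- Grade AST, ALT and bilirubin on multiples of baseline when baseline is above ULN, as in Table 6-8. Keep the ULN bands otherwise.
- Leave GGT as it is. Do not add an automatic upgrade for symptomatic lipase or amylase, because the documents describe no field that links a laboratory result to an AE.
- Correct the table number in the cross-reference.

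The cost is a table edit, a footnote and minor programming on baseline values already collected. No protocol treatment rule changes. The small downside is that symptomatic lipase or amylase values above 2 x ULN would be graded one lower in the laboratory data than in the AE data, which the footnote discloses.

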10.5 Appendix E Definitions

ORR

Objective response rate is defined as the percentage of patients who have at least one confirmed response of CR or PR defined by RECIST 1.1 prior to any evidence of progression.

DoR

Duration of response will be defined as the time from the date of first documented response, (that is subsequently confirmed) until date of documented progression or death in the absence of disease progression, the end of response should coincide with the date of progression or death from any cause used for the PFS endpoint. The time of the initial response will be defined as the latest of the dates contributing towards the first visit response of PR or CR.

DCR

Disease control rate is defined as the proportion of subjects with advanced tumors among whom achieve a best overall response CR/PR/SD after treatment with HH2710.

PFS

PFS is defined as the time from date of first dosing until the date of objective disease progression as defined by RECIST 1.1 or death (by any cause in the absence of progression) regardless of whether the subject withdraws from HH2710 treatment or receives another anticancer therapy prior to progression.

Overall Survival

Overall survival is defined as the interval between the date of first dose and the date of patient death due to any cause. Patients who have not died at the time of the statistical analysis will be censored at the time they were last known to be alive.

TTR

TTR is defined as the duration from the first day of study treatment until the first documented response (CR or PR).

TPP

TPP is defined as the duration from the first day of study treatment until the first documented progression (PD).

Baseline

For data analyses, baseline will be defined as the value measured on day 1 of the start of HH2710. The protocol specifies that all study procedures on day 1 should be completed before the initiation of HH2710 which will be the assumption in the analysis unless the time of the assessment is recorded. If a day 1 value is not available, the latest value before the day of the start of HH2710 may be used.

End of Treatment Date

The end of HH2710 therapy date is the date the decision was made to end investigational product reported on the end of investigational product administration CRF.

End of Study

For a subject: a subject ends the study when they die, consent is withdrawn, or they are lost to follow-up. The end of study date will be captured on the end of study CRF.

For the study as a whole: the end of study as a whole is defined as a minimum of 80% of patients in the Phase II stage have died, have been lost to follow-up, or have been followed for survival for minimum 12 months after the first dose of study treatment.

Treatment-emergent Adverse Event

TEAE are defined as AEs that were reported or worsened on or after the start of study drug dosing and up to the safety follow-up.

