5.2 Inclusion criteria

Patients eligible for inclusion in this study must meet all of the following criteria:

1. Provide signed and dated informed consent prior to initiation of any study-related procedures;
2. Male or female patients aged ≥ 18 years;
3. Phase I dose escalation stage: Patients who have been diagnosed with histologically or cytological documented, unresectable/metastatic tumors that are refractory or intolerant to standard therapy or for whom no curative standard therapy exists.
 - For LCH/ECD: Eligible patients must have multifocal disease and the diagnosis must be confirmed by pathological evaluation of the affected tissue.
4. For Phase I expansion stage and Phase II stage: Histologically or cytologically documented unresectable/metastatic tumors with evidence of genetic mutations affecting MAPK

pathway is required. Patients with a BRAF V600 mutation must have progressed on or after standard therapy, including BRAF and/or MEK inhibitors (≤ 3 lines). Patients entering the Phase 2 portion of the trial will be enrolled in Cohorts 1-4 depending upon their tumor types.

- Cohort 1: Patients with *BRAF/NRAS* (mutation sites including: *NRAS G13V, NRAS Q61, BRAF V600, BRAF G469A, L485W, L597Q, T599dup*) mutated melanoma;
- Cohort 2: Patients with *BRAF/NRAS* (mutation sites including: *NRAS G13V, NRAS Q61, BRAF V600, BRAF G469A, L485W, L597Q, T599dup*) mutated non-small cell lung cancer;
- Cohort 3: Patients with *BRAF V600* mutated Langerhans Cell Histiocytosis Syndrome (LCH)/ Erdheim-Chester disease (ECD);
 - For LCH/ECD: Eligible patients must have multifocal disease and the diagnosis must be confirmed by pathological evaluation of the affected tissue.
- Cohort 4: Patients with *RAS/RAF/MEK/ERK* mutated tumor types that are not included in other cohorts.

5. Patients in the Phase I dose escalation portion of the trial may have measurable (per RECIST v1.1) or evaluable disease. Patients in the Phase I dose expansion and Phase II portions of the trial must have measurable disease per RECIST v1.1.

6. Eastern Cooperative Oncology Group (ECOG) performance status ≤ 1 .

7. Predicted life expectancy ≥ 3 months;

8. Adequate renal function defined as a creatinine clearance ≥ 60 mL/min (using Cockcroft-Gault formula, see [Appendix 14.3](#));

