10.2 Analysis sets

10.2.1 All-Treated Set

The All-treated set includes all patients who have received at least one dose of study medication. This set will be used for efficacy analysis.

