Best response determination in trials where confirmation of complete or partial response IS NOT required: Best response in these trials is defined as the best response across all time points (for example, a patient who has SD at first assessment, PR at second assessment, and PD on last assessment has a best overall response of PR). When SD is believed to be best response, it must also meet the protocol specified minimum time from baseline. If the minimum time is not met when SD is otherwise the best time point response, the patient's best response depends on the subsequent assessments. For example, a patient who has SD at first assessment, PD at second and does not meet minimum duration for SD, will have a best response of PD. The same patient lost to follow-up after the first SD assessment would be considered not evaluable.

Best response determination in trials where confirmation of complete or partial response IS required: Complete or partial responses may be claimed only if the criteria for each are met at a subsequent time point as specified in the protocol (generally 4 weeks later). See the following table for further information.

Best Overall Response when Confirmation of CR and PR Required

Overall response First time point	Overall response Subsequent time point	Best overall response
CR	CR	CR
CR	PR	SD, PD or PR ^a

CR	SD	SD provided minimum criteria for SD duration met, otherwise, PD
CR	PD	SD provided minimum criteria for SD duration met, otherwise, PD
CR	NE	SD provided minimum criteria for SD duration met, otherwise, NE
PR	CR	PR
PR	PR	PR
PR	SD	SD
PR	PD	SD provided minimum criteria for SD duration met, otherwise, PD
PR	NE	SD provided minimum criteria for SD duration met, otherwise, NE
NE	NE	NE

Note: CR = complete response, PR = partial response, SD = stable disease, PD = progressive disease, and NE = not evaluable. a: If a CR is truly met at first time point, then any disease seen at a subsequent time point, even disease meeting PR criteria relative to baseline, makes the disease PD at that point (since disease must have reappeared after CR). Best response would depend on whether minimum duration for SD was met. However, sometimes 'CR' may be claimed when subsequent scans suggest small lesions were likely still present and in fact the patient had PR, not CR at the first time point. Under these circumstances, the original CR should be changed to PR and the best response is PR.

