6.1 Full Analysis Set (FAS)

The Full Analysis Set includes all patients who have received at least one dose of study medication. This set will be used for efficacy analysis.

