8.7 Efficacy Analyses

The efficacy analysis will be based on full analysis set.

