8.7.1.1 Best Overall Response

Best Overall Response (BOR) is defined as the best overall response recorded from the start of treatment until disease progression or initiation of alternative therapy or end of study. A summary of subjects achieving a best overall response in a given category (CR, PR, SD, PD, NE, and Missing) will be provided.

In phase II, BOR will be summarized by investigator.

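### DCR counts stable disease of any duration, and the SAP's best-response list has no place for non-progressing patients without measurable disease

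*SAP*

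**What the plan says.** **DCR.** SAP Appendix E: "Disease control rate is defined as the proportion of subjects with advanced tumors among whom achieve a best overall response CR/PR/SD after treatment with HH2710". SAP 8.7.1.3 estimates it by the same method as ORR. It is secondary in Phase II and exploratory in Phase I (SAP 4.1).

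**Best overall response.** SAP 8.7.1.1 takes the best response from start of treatment to progression, alternative therapy or end of study, and tabulates "best overall response in a given category (CR, PR, SD, PD, NE, and Missing". It gives no minimum SD time and no Non-CR/non-PD category.

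**RECIST text.** Protocol Appendix 1: "When SD is believed to be best response, it must also meet the protocol specified minimum time from baseline". Where CR and PR need confirmation, as they do here (Protocol 7.2.5), five rows of its best-response table also depend on that minimum. For patients with non-target lesions only, it lists CR, Non-CR/non-PD, not evaluated and PD. It prefers Non-CR/non-PD and advises against SD when nothing can be measured.

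**Scans.** Screening, Cycle 3 Day 1 (Day 43), every two cycles, and end of treatment (Protocol 7.2.5), with a 7-day window either side (Protocol 7.1). The end-of-treatment visit falls within 7 days of the last dose (Table 7-1).

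**Eligibility.** Under Protocol 5.2 item 5, escalation patients "may have measurable (per RECIST v1.1) or evaluable disease". Expansion and Phase II patients must have measurable disease.

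**SD durations elsewhere.** Only in the cohort 1 and 2 decision rule: 6 months in Protocol 4.1 and 10.4, 6 weeks in SAP 3.2 and 5.

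**The concern.** The SAP's rules cannot be programmed for DCR without choices that neither document makes.

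First, Appendix 1 leaves the minimum SD time to the protocol, and the protocol never sets it for best response or DCR. Read literally, the SAP credits disease control for one SD scan taken at any time after the first dose. Patients who stop very early are scanned at end of treatment, so the rule can credit drug activity to those with least exposure.

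Second, an escalation patient with evaluable disease only, who neither progresses nor reaches CR, has no matching category in the SAP's closed list. Whoever programs the table must decide whether that patient is SD (a DCR success), NE (a failure) or something else.

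At stake is a descriptive activity measure computed on very small groups, in a study that SAP section 7 says was terminated early with fewer patients than planned.

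**Working it through.** Neither document states an expected DCR, so there is no figure to reproduce. The check sets the rules side by side and then sizes the effect.

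**1. Early SD.** Take a hypothetical patient whose last dose is Day 10. The end-of-treatment scan is due by Day 17, which is 16 days after first dose. It shows SD, and new therapy then starts, which closes the SAP's best-response window. The SAP gives best response SD and a DCR success. Under a 6-week minimum (42 days), 16 < 42, so SD is not met; with no later assessment, Appendix 1's own example for loss to follow-up points to NE. Removing a minimum can add successes but never remove them, so the direction is upward only.

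**2. Who is affected under 6 weeks.** Cycle 3 Day 1 is Day 43, and 43 − 1 = 42 days after first dose, so an on-time first scan already meets 6 weeks. Allowing the 7-day window, 42 − 7 = 35 days (Day 36). Only early end-of-treatment or unscheduled scans with no later qualifying SD are then excluded. The origin matters too: counted from a baseline scan 28 days before first dose, a scan 14 days after it would already reach 28 + 14 = 42 days.

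**3. Unconfirmed responses.** PR at Day 43 followed by PD is SD in Appendix 1 if the minimum is met, otherwise PD. At 6 weeks it is a DCR success; at 6 months it is a failure.

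**4. No measurable disease.** Appendix 1's category for the non-progressing patient without CR is Non-CR/non-PD, which the SAP list lacks. Entering it as SD raises DCR. Entering it as NE leaves the patient uncounted.

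**5. Effect of one patient** (100/n points).
- Escalation dose levels at the January 2022 cutoff (n = 3 or 4): 33.3 or 25.0.
- 600 mg QD with its 4 expansion patients pooled (n = 8): 12.5.
- Phase II at planned size, where only the SD-time issue applies: n = 9, 11.1; n = 27, 3.7; n = 36, 2.8.

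**6. Illustration, N = 22 escalation patients.** The counts are assumed: c = 10 with CR, PR or SD of adequate duration; s = 3 with short SD only; m = 4 Non-CR/non-PD. DCR = (c + s if short SD counts + m if Non-CR/non-PD counts)/N.
- Neither counted: 10/22 = 45.5%
- Short SD only: 13/22 = 59.1%
- Non-CR/non-PD only: 14/22 = 63.6%
- Both: 17/22 = 77.3%

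With s = m = 0, all four equal 45.5%.

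**7. ORR, for the optional analysis.** If no patient without measurable disease has a CR, all-treated ORR = measurable-disease ORR × (1 − f), where f is the share without measurable disease. Assuming 4 responders and 4 such patients: 4/22 = 18.2% (Clopper-Pearson 95% CI 5.2 to 40.3) against 4/18 = 22.2% (6.4 to 47.6). At f = 0 they coincide.

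**The case against.** Several counterarguments have force.

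- **Status of the RECIST text.** The SAP has no RECIST appendix; the text is the protocol's and is marked as a translation for reference. True, but Protocol 7.2.5 sends assessors to it, and the SAP defines response by the same criteria: "Objective response rate is defined as the percentage of patients who have at least one confirmed response of CR or PR defined by RECIST 1.1". The minimum SD time is also left to the protocol to supply, and it does not.
- **Few patients may be affected.** Under 6 weeks an on-time first scan qualifies. This stands and limits the size; it does not supply the missing rule.
- **Scope.** SAP 8.7.1.4 sends exploratory efficacy analyses to separate documents, and Phase I ORR and DCR are exploratory. Yet SAP 8.7.1.2 reports ORR by treatment group, which SAP 8.1 defines to include Phase I dose levels. Coverage is therefore unclear. SAP section 7 adds that many analyses may not be run. The Phase II DCR definition is affected regardless.

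Three stronger readings are tempting and are not supported.

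- **That all-treated ORR breaches RECIST.** The SAP says "The Full Analysis Set includes all patients who have received at least one dose of study medication. This set will be used for efficacy analysis", matching Protocol 10.2.1: "The All-treated set includes all patients who have received at least one dose of study medication. This set will be used for efficacy analysis". Appendix 1 restricts entry to measurable disease only where response is the primary endpoint. Phase I ORR is exploratory, and a patient with non-target lesions only can still have a CR. Dilution is possible, but no document shows that any enrolled patient lacked measurable disease.
- **That DCR is wrong in both directions.** The missing SD time biases upward only. The missing category leaves a mapping undefined, which is not a demonstrated error of either sign.
- **That patients without measurable disease cannot be SD and must fall to NE.** Appendix 1 advises against SD rather than forbidding it, and keeps not evaluated for incomplete assessment.

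**Conclusion.** The point holds on two counts. As written, DCR accepts SD of any duration, which can only bias it upward relative to any minimum, in Phase II as well as Phase I. The best-response list also omits the category that Appendix 1 assigns to non-progressing patients without measurable disease, so their DCR status is undefined and could shift the rate either way.

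The size cannot be fixed from the documents: neither the number of early SD patients nor the number without measurable disease is given, and both could be zero. One patient is worth 25 to 33 points at an escalation dose level of 3 or 4, and about 3 points in a full Phase II cohort of 36. The 45.5% to 77.3% span rests wholly on assumed counts, and the 22 patients predate the 300 mg QD and 200 mg BID cohorts. This should be corrected before any DCR is reported, but it does not touch the primary ORR definition.

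**What to change.** - **(a) Minimum SD time.** In SAP 8.7.1.1 and Appendix E, set a minimum for best response SD and hence DCR, with its origin stated and tied to the first scheduled scan. One option is the SAP's own 6 weeks less the 7-day window, 35 days from first dose. Assign shorter SD to NE or PD as in Appendix 1, and apply the same minimum to the unconfirmed-response rows. Reconcile it with the 6-week (SAP) and 6-month (protocol) SD durations in the decision rule, or say why they differ.
- **(b) Non-CR/non-PD.** Add it as a separate best-response category, state whether it counts towards DCR, and show DCR with and without it. Neither document decides this, so both figures are needed.
- **(c) Optional.** Keep all-treated ORR as the pre-specified Phase I figure and add ORR in patients with measurable disease at baseline, labelled supplementary because it comes after the decision to stop. State whether SAP 8.7.1.4 removes Phase I ORR and DCR from this SAP.

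**Cost.** SAP wording and slightly more programming, with no new assessments, assuming the database holds target and non-target responses by visit. DCR may fall under the minimum SD time, or rise if Non-CR/non-PD is counted.
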